4.2.3. Recurrence-free survival at 3 et 5 years in arm C+LT

The recurrence-free survival at 3 years is defined as follows:

- If the patient experiences one or more recurrences before the cut-off date, and the first recurrence occurs within 3 years post-randomization: Time between randomization and the occurrence of the first recurrence.
- If the patient dies before the cut-off date without experiencing recurrence, and the death occurs within 3 years post-randomization: Time between randomization and death, regardless of the cause.
- If the patient is alive without recurrence at the cut-off date: Time between randomization and the date of the last update. The last update date will be a maximum of 3 years post-randomization.

The recurrence-free survival at 5 years is defined similarly but at 5 years. The analysis will be conducted in patients randomized to Arm C+LT and who underwent LT.

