2.2. Secondary objectives

- Compare overall survival at 3 years between the two arms.
- Compare progression-free survival at 3 years and 5 years between the two arms.
- Evaluate recurrence-free survival at 3 years and 5 years in arm C + LT.
- Evaluate the recurrence rate at 3 years and 5 years in arm C + LT.
- Compare the quality of life between the two arms.

3. Definition of the study populations

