4.2.2. Comparison of progression-free survival at 3 and 5 years

In Arm C, progression is defined as the first progression occurring after randomization. In Arm C+LT, progression is defined as the first recurrence occurring after liver transplantation (LT).

The progression-free survival at 3 years is defined as follows:

- If the disease progresses one or more times before the cut-off date, and the first progression occurs within 3 years post-randomization: Time between randomization and the occurrence of the first progression.
- If the patient dies before the cut-off date without experiencing progression, and the death occurs within 3 years post-randomization: Time between randomization and death, regardless of the cause.
- If the patient is alive without progression at the cut-off date: Time between randomization and the date of the last update. The last update date will be a maximum of 3 years post-randomization.

The progression-free survival at 5 years is defined similarly but at 5 years. The analysis will be conducted in the PP population.

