6.6. Imputation

When a date is incomplete because only the day is missing, it will be imputed to the 15th of the month.

For the variable 'number of CRLM in quantitative form, regardless of the evaluation time, the following imputation will be performed: When the number in the category is strictly greater than 20, the number of nodules in quantitative form is uncountable. The number of nodules in quantitative form is then imputed as 25. This imputation will be done even in the case where a specific number of nodules is provided and that number is strictly greater than 25.

For the variables 'number of CRLM at inclusion', 'diameter of the largest CRLM at inclusion', 'Fong score at inclusion', the following imputation will be performed: The information is that provided at the last evaluation before randomization. When this data is not available, the information taken into account is that provided at the inclusion CT scan, and failing that, at the inclusion MRI.

For the ACE and CA19-9 markers at inclusion, the following imputation will be performed: The information is that provided at the last evaluation before randomization. When this data is not available, the information taken into account is that provided at inclusion.

For the ACE and CA19-9 markers at D0, the following imputation will be performed: The information is that provided at D0. When this data is not available, the information taken into account is that provided during the last assay in the month preceding transplantation.

Patients in arm C+LT who have undergone transplantation and have the chemotherapy type = NA are considered as not receiving adjuvant chemotherapy.

7. Interim analyses

No interim analysis is planned in this study

8. Sample size

The number of required events is 29. It aims to demonstrate a 40% difference in overall 5-year survival between the two randomization arms (50% for arm C+LT versus 10% for arm C) with a power of 90%, a two-sided alpha of 5%, and a follow-up loss rate of 2% and 10% in the C+LT and C arms, respectively. When we noticed that some patients in the C+LT arm did not receive LT, we re-estimated the number of events to 50 assuming that patients without LT would have a 10% survival rate and that patients with LT would have a 50% survival rate.

9. Statistical report

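### RFS in arm C+LT is timed from randomisation but only in patients who were later transplanted, so the wait for LT is immortal time and post-LT RFS is overstated

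*SAP*

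**What the plan says.** Section 2.2 lists two descriptive secondary objectives for the transplant arm: "Evaluate recurrence-free survival at 3 years and 5 years in arm C + LT" and "Evaluate the recurrence rate at 3 years and 5 years in arm C + LT".

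Section 4.2.3 defines the RFS time for a patient who recurs as follows: "the first recurrence occurs within 3 years post-randomization: Time between randomization and the occurrence of the first recurrence". Deaths without recurrence are also timed from randomisation, and so is the limit on follow-up: "The last update date will be a maximum of 3 years post-randomization". The 5-year version follows the same pattern: "The recurrence-free survival at 5 years is defined similarly but at 5 years". The analysis set is then fixed: "The analysis will be conducted in patients randomized to Arm C+LT and who underwent LT".

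Section 4.2.3 does not define recurrence further. Section 4.2.2 does so for this arm: "In Arm C+LT, progression is defined as the first recurrence occurring after liver transplantation (LT". Section 4.2.4 counts recurrences in windows of 3 and 5 years after randomisation, again in transplanted patients only.

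Section 6.4 plans Kaplan-Meier for both endpoints, with no delayed entry or landmark, and no comparison for RFS. Section 8 shows that not everyone in the arm was transplanted: "When we noticed that some patients in the C+LT arm did not receive LT, we re-estimated the number of events to 50".

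**The concern.** Membership of the RFS set depends on something that happens after time zero. A patient enters only by surviving to LT, but the clock has been running since randomisation. Death before LT is excluded by the choice of set, and recurrence before LT is excluded by the definition in section 4.2.2. The interval from randomisation to LT is immortal time.

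The resulting figure answers neither natural question:

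- **How do patients fare after LT?** Each patient's wait is added to the recurrence-free time, so the estimate is too favourable.
- **How does the arm fare from randomisation?** The patients never transplanted are missing. Section 8 itself assumes that they survive less often (10% against 50%).

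For a single-arm descriptive endpoint the estimate is the whole result, so a built-in shift in the favourable direction goes straight into what is reported.

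**Working it through.** **The plan's own figures.** The SAP states no RFS or recurrence rate and no interval from randomisation to LT, so there is nothing to reproduce for this endpoint. Its 29 required events do reproduce, assuming 1:1 allocation: HR = ln 0.5 / ln 0.1 = 0.301, and Schoenfeld's formula gives 29.2. That number has no bearing here.

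**Direction.** Let w be the wait from randomisation to LT and R the time from LT to recurrence or death. In the analysed set the SAP's time is w + R. Since w ≥ 0, P(w + R > 36 months) ≥ P(R > 36 months). No distributional assumption is needed.

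**Does the SAP bound the wait?** No. The 3-month limit in section 3.1 runs from the last chemotherapy cycle to LT. Breaching it is a major deviation, but it does not remove a patient from the RFS set.

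**Size, post-LT reading.** Assumptions: constant hazard from LT, h = −ln(S36)/36, where S36 is the true 3-year post-LT RFS; fixed wait w of 1, 3 or 6 months. The true value at T months is exp(−hT); the SAP reports exp(−h(T − w)). For S36 = 30%, h = 1.204/36 = 0.0334 per month, and w = 3 gives exp(−0.0334 × 33) = 33.2%.

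| Horizon | True RFS | w = 1 | w = 3 | w = 6 |
|---|---|---|---|---|
| 3 years | 20% | 20.9% | 22.9% | 26.2% |
| 3 years | 30% | 31.0% | 33.2% | 36.7% |
| 3 years | 50% | 51.0% | 53.0% | 56.1% |
| 5 years | 6.8% | 7.2% | 7.8% | 8.9% |
| 5 years | 13.4% | 13.9% | 14.9% | 16.4% |
| 5 years | 31.5% | 32.1% | 33.4% | 35.4% |

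The overstatement at 3 years is about 1, 3 or 6–7 points; at 5 years it is 0.3 to 3.9 points.

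Hazard shape matters somewhat. With S36 = 30% and w = 3, a Weibull shape of 0.7 (early events) gives +2.2 points and a shape of 1.3 gives +4.1, against +3.2 for constant hazard.

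**Size, as-randomised reading.** Suppose a share p is never transplanted and all of them have an event by 3 years, which gives an upper bound on the gap. The event-free share is then (1 − p) × exp(−h(36 − w)). With S36 = 30% and w = 3, this is 0.9 × 33.2% = 29.8% for p = 10% and 0.8 × 33.2% = 26.5% for p = 20%. The reported 33.2% is 3.3 or 6.6 points higher.

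A simulation with exponentially distributed waits (mean 2, 3 or 6 months) and 20% lost before LT, each loss counted as an event, shows the SAP figure above both alternatives:

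| Mean wait | SAP figure | Post-LT RFS | All randomised |
|---|---|---|---|
| 2 months | 31.6% | 30% | 25.3% |
| 3 months | 32.6% | 30% | 26.1% |
| 6 months | 35.6% | 30% | 28.5% |

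**Recurrence rate (section 4.2.4).** Let d be the share of the hazard due to death without recurrence, assumed 10%, with S36 = 30% and T = 36.

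- True cumulative incidence from LT: (1 − d)(1 − exp(−hT)) = 0.9 × 0.70 = 63.0%.
- SAP method, taken as 1 − KM censoring such deaths: 1 − exp(−h(1 − d)(T − w)) = 65.1%, 63.0% or 59.5% for w = 1, 3 or 6.
- Clock moved to LT, 1 − KM kept: 1 − exp(−h(1 − d)T) = 66.2%, which is 3.2 points too high.

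The late clock lowers the rate and the censoring of deaths raises it. At w = 3 they happen to cancel, so no net direction can be claimed. Correcting the clock alone would expose the upward error.

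**The case against.** The strongest defence is that the SAP never calls the figure post-LT. Sections 4.2.3 and 4.2.4 refer to randomisation in every time, limit and window, matching the origin used for overall and progression-free survival. Read literally, RFS is the share of transplanted patients alive and recurrence-free 3 years after randomisation, which is a defined quantity. Restricting the set to transplanted patients is also reasonable, because recurrence after LT has no meaning without LT. Stating the time origin plainly and reporting the interval to LT would remove much of the risk of misreading.

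The restriction is indeed defensible; the clock attached to it is not. The literal quantity conditions on a later event and describes neither the course after LT nor the randomised arm. A label would make that visible without making the number useful. Consistency with the comparative endpoints is not needed in a single-arm description.

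Four points stand:

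- Certainty of direction belongs to the post-LT reading. The as-randomised reading needs an assumption about untransplanted patients.
- The size is assumed throughout. For waits up to 3 months it is roughly 1 to 4 points, against a 95% half-width of about 13 to 16 points around 30% if 30 to 50 patients are transplanted (also an assumption).
- Competing risks are a separate issue from immortal time. They enter here because changing the clock without them would not correct the recurrence rate.
- No test and no alpha is affected.

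**Conclusion.** The concern holds. Time origin and analysis set in section 4.2.3 do not fit together, and the RFS it yields is at or above the true post-LT RFS whatever the event distribution. The size depends on a wait that the SAP does not give: modest at 1 to 3 months and material at 6 months, under the constant-hazard assumption. Section 4.2.4 shares the mismatch, but its net error may go either way. The consequence is confined to two descriptive secondary endpoints. It should be corrected, but it does not threaten the trial's main conclusion.

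**What to change.** **RFS (4.2.3).** Keep the set of transplanted patients randomised to C+LT. Start the clock at the date of LT, and replace the limits of 3 and 5 years from randomisation with 3 and 5 years from LT, using all available follow-up.

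**Recurrence rate (4.2.4 and 6.4).** Use the same origin and set, and replace Kaplan-Meier with an Aalen-Johansen cumulative incidence estimate in which death without recurrence is a competing event.

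**If a 5-year figure from randomisation is wanted.** Report alongside it event-free survival in everyone randomised to C+LT, counting progression and death before LT as events, and label it as a different endpoint.

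**Cost.** The real downside is the 5-year post-LT estimate. Section 4.1 limits follow-up for overall survival to 60 months from randomisation. If no later data exist, post-LT follow-up ends at 59, 57 or 54 months for waits of 1, 3 or 6 months, and that stated objective cannot be met. In that case, report the 3-year estimate and the latest supportable post-LT time, with numbers at risk. The 3-year estimate needs only 37, 39 or 42 months from randomisation.

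The rest is SAP wording, one derived time variable and a cumulative incidence routine. Section 5.6 already describes complications by time since LT, so the LT date is needed anyway. Reported RFS will be somewhat lower. Section 10 requires the SAP to be validated before the database is frozen, so the change belongs before that point.

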4.2.4. Recurrence rate at 3 et 5 years in arm C+LT

Recurrence at 3 years is defined as the occurrence of any recurrence, regardless of the site, within 3 years post-randomization. Recurrence at 5 years is defined as the occurrence of any recurrence, regardless of the site, within 5 years post-randomization. The analysis will be conducted in patients who underwent LT.

4.2.5. Quality of life

Two questionnaires, QLQ-C30 and QLQ-LMC21, are completed in both arms. A third questionnaire, NIDDK, is completed only in arm C+LT.

5. Description

5.1. Patients characteristics at the time of Colorectal Liver Metastases (CRLM) diagnosis

Description of characteristics by randomization arm. This analysis will include all patients from the ITT population.

5.2. Characteristics at the inclusion

Description of characteristics at enrolment by randomization arm. The analysis will include all patients from the ITT population.

5.3. Recipient and donor characteristics at LT

This analysis will focus on patients who underwent LT.

5.4. Type of recurrence and treatments in arm C+LT

The analysis will focus on patients who underwent liver transplantation (LT). Only the first recurrence will be described.

5.5. Treatments received in arm C post randomization

The analysis will focus on patients randomized to arm C and who had at least one post-randomization visit.

5.6. Tolerance

The toxicity of chemotherapy, the occurrence of adverse events and the complications occurring within 3 months post-LT will be described.

6. Statistical aspect

6.1. Description

Quantitative variables will be described using the mean, standard deviation, minimum, maximum, median, first quartile, and third quartile. Qualitative or categorical variables will be described using frequencies and percentages.

6.2. Comparison of characteristics at randomization

The patient characteristics at randomization will be compared using the Student's t-test or Wilcoxon-Mann-Whitney test for quantitative variables and the chi-squared test or Fisher's exact test for qualitative variables.

6.3. Primary analysis

The evaluation of overall survival will be conducted by constructing survival curves using the Kaplan-Meier method. Graphs will be created following the best practices defined by Pocock³.

- If the proportionality of hazards is respected: Survival in each randomization arm will be compared using the Log-Rank test. The hazard ratio and the associated 95% confidence interval will be estimated using a Cox proportional hazards model.
- If the proportionality of hazards is not respected: the difference in Restricted Mean Survival Time (RMST) between the arms and the associated 95% confidence interval will be estimated.

The randomization stratification by cluster of centers will not be taken into account in the analyses. This is because it was done for administrative reasons.

6.4. Secondary analyses

- The comparison of overall survival at 3 years will be conducted using the same method as for the primary objective. The Kaplan-Meier curve will not be redrawn (refer to the Kaplan-Meier curve of the primary objective).
- The comparison of progression-free survival at 3 and 5 years will be conducted using the same method as for the primary objective.
- The evaluation recurrence-free survival at 3 and 5 years will be conducted by constructing survival curves using the Kaplan-Meier method. No comparison will be made.
- The recurrence rate will be described at 3 and 5 years. It will be calculated using the Kaplan-Meier method.
- Quality of life will be compared between randomization arms using a repeated measures model if the data allow.

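### Kaplan-Meier is the wrong estimator for the recurrence rate in transplanted patients: it censors deaths without recurrence, so if any occur it overstates recurrence at 3 and 5 years

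*SAP*

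**What the plan says.** Three parts of the SAP bear on this.

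- **Definition, section 4.2.4.** "Recurrence at 3 years is defined as the occurrence of any recurrence, regardless of the site, within 3 years post-randomization"; the 5-year outcome is worded the same way. Death is not part of the event. On the population: "The analysis will be conducted in patients who underwent LT".
- **Estimator, section 6.4.** "The recurrence rate will be described at 3 and 5 years. It will be calculated using the Kaplan-Meier method".
- **Deaths without recurrence, section 4.2.3.** RFS has its own rule for these patients, which begins "If the patient dies before the cut-off date without experiencing recurrence, and the death occurs within 3 years post-randomization" and makes the death an event. Section 6.4 also assigns Kaplan-Meier to RFS, where it is appropriate because death is part of the event.

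The SAP does not say how a death without recurrence is handled in the recurrence rate. It names no competing-risk or cumulative incidence method anywhere.

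**The concern.** A patient who dies without recurrence can no longer recur. Kaplan-Meier censors that patient and lets those still at risk stand in for them, as though recurrence were still possible. The result describes recurrence in a hypothetical setting where nobody dies of anything else. Section 4.2.4 asks something different: how many transplanted patients have a recurrence within 3 and 5 years.

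Two things are at stake. The reported rate would be too high whenever such a death precedes a later observed recurrence. It would also fail to fit the RFS result: recurrence rate plus the proportion dead without recurrence would exceed 1-RFS. A reader who subtracts the recurrence rate from 1-RFS would understate deaths without recurrence.

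Such deaths are plausible here. The planning assumption in section 8 is 5-year survival of "50% for arm C+LT versus 10% for arm C", so about half of the patients in arm C+LT are expected to die by 5 years. The SAP does not give the split between deaths before and after recurrence.

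**Working it through.** The SAP states no recurrence figure, so there is none to reproduce.

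**Inputs.** From the SAP: the event (recurrence only), the clock (randomization), the horizons (36 and 60 months) and the estimator (Kaplan-Meier). Assumed: a 5-year 1-KM value R of 50, 60 or 70%, and an actual proportion D of 5, 10 or 15% dead without recurrence by 5 years. Follow-up is taken as otherwise complete.

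**Formulas, constant hazards.** Let a be the hazard of recurrence, b the hazard of death without recurrence, and T = 60 months.

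- a = -ln(1-R)/T
- b solves D = b/(a+b) × (1 - exp(-(a+b)T))
- 1-KM(t) = 1 - exp(-a·t)
- Cumulative incidence of recurrence: CIF(t) = a/(a+b) × (1 - exp(-(a+b)t))
- Gap = 1-KM(t) minus CIF(t)

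**Early-death limit.** If all deaths without recurrence come before any recurrence, CIF(t) = (1-D) × (1-KM(t)), so the gap is D × (1-KM(t)).

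**Overstatement at 5 years, in percentage points (early-death limit in brackets):**

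| 5-year 1-KM | D = 5% | D = 10% | D = 15% |
|---|---|---|---|
| 50% | 1.55 (2.5) | 3.13 (5.0) | 4.74 (7.5) |
| 60% | 1.96 (3.0) | 3.97 (6.0) | 6.01 (9.0) |
| 70% | 2.44 (3.5) | 4.93 (7.0) | 7.47 (10.5) |

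At 3 years, 1-KM is 34.0, 42.3 and 51.4% for R = 50, 60 and 70%. The gaps run from 0.67 points (R = 50%, D = 5%) to 3.72 points (R = 70%, D = 15%), and from 1.70 to 7.72 points in the early-death limit.

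**One case in full, R = 70% and D = 10%.**

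- a = -ln(0.30)/60 = 0.02007 per month, and b = 0.00308 per month.
- CIF(60) = 0.02007/0.02315 × (1 - exp(-0.02315 × 60)) = 65.07%.
- 1-RFS at 60 months = 1 - exp(-0.02315 × 60) = 75.07%.
- Cumulative incidence fits RFS: 65.07% + 10% = 75.07%.
- 1-KM does not: 70% + 10% = 80%. Subtracting it from 1-RFS gives 75.07% - 70% = 5.07% dead without recurrence, when the true figure is 10%.

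A simulation of 1,000,000 patients gave 1-KM 69.99%, recurrence 65.03%, dead without recurrence 10.03% and RFS 24.94%.

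**In whole numbers.** Of 40 transplanted patients, 4 die before anyone recurs and 24 of the other 36 recur, all with full follow-up. The proportion with recurrence is 24/40 = 60%. 1-KM is 24/36 = 66.7%.

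**The other ordinary reading.** If deaths were counted as events, the result would simply be 1-RFS. In the full case above that is 75.07% against 65.07%, a larger overstatement. Both readings err upward.

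**Sampling error for comparison.** With 30 to 50 transplanted patients (assumed), the 95% CI half-width around 65% is 1.96 × √(0.65 × 0.35/n): 17.1 points at n = 30 and 13.2 points at n = 50.

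**The case against.** Four points can be made for the plan.

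1. **The SAP never says that deaths are censored.** If patients who die without recurrence were kept at risk up to the horizon, and nobody else were censored early, the calculation would return exactly the proportion with recurrence. This is true, but it is not ordinary Kaplan-Meier and the SAP does not specify it. A statistician following section 6.4 would censor at death.

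2. **1-KM may rightly differ from the crude proportion.** Once living patients are censored before the horizon, the two differ even with no deaths at all. This stands as a clarification. The right comparator is the cumulative incidence estimate, which coincides with 1-KM when nobody dies without recurrence.

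3. **The size is assumed, and late deaths shrink it.** For deaths all at month u, the 5-year gap is D × (1 - KM(60)/KM(u)). With R = 70% and D = 10%, deaths at month 48 give about 2.1 points at 5 years and none at 3 years; deaths near month 60 give about zero. This stands: for that case the 5-year range is 0 to 7 points, depending on timing.

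4. **Little depends on it.** The outcome is descriptive, in one arm, with no test or decision attached. RFS already counts these deaths, and even the largest gap shown (10.5 points) is below the assumed sampling error. This stands as a limit on importance. It does not justify the estimator: a confidence interval displays sampling error, whereas this bias always runs in the same direction and no interval shows it.

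**Conclusion.** The concern holds. Section 6.4 names an estimator that does not match the quantity defined in section 4.2.4, and nothing elsewhere in the SAP repairs it.

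The direction is certain: upward whenever a death without recurrence precedes a later observed recurrence, and zero otherwise. The size cannot be fixed from the SAP. Under the assumed rates it is 1.5 to 7.5 points at 5 years and 0.7 to 3.7 points at 3 years with constant hazards. If all such deaths come first, it is 2.5 to 10.5 and 1.7 to 7.7 points. If they come late, it falls towards zero. Constant hazards from randomization are a simplification, since the patients analysed must first survive to transplantation.

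This should be corrected, but it does not threaten the trial's main conclusions. It affects one secondary descriptive outcome in one arm; overall, progression-free and recurrence-free survival are untouched.

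**What to change.** In section 6.4, replace the Kaplan-Meier sentence for the recurrence rate with one stating that:

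- recurrence within 3 and 5 years of randomization is estimated by the cumulative incidence function (Aalen-Johansen) with a 95% CI;
- death without recurrence is a competing event, and only patients alive without recurrence are censored;
- the cumulative incidence of death without recurrence is shown beside it.

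Keep Kaplan-Meier for RFS. In the same patients, the two cumulative incidences then add up to 1-RFS.

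The cost is one sentence. The recurrence and death dates are already needed for RFS under section 4.2.3, so no further data are required. If no patient dies without recurrence, the result equals 1-KM and nothing is lost. Section 10 requires the SAP to be validated before the database is frozen, so the change belongs in the SAP before that point.
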